#### 7.2.4.5 Ability to Perform Daily Activities

Whether or not subjects are able to perform their usual daily activities is assessed by subject responses (Yes or No) in the eDiary to the question, "Do you feel able to perform your usual daily activities?" If a subject responds "Yes" but has used a rescue medication, the subject is considered as not being able to perform the usual daily activities.

Protocol: CP-2019-001 Page 17 of 26 Final Version 1.0

# 7.3 Safety Assessments

Safety will be assessed by:

- AEs and serious adverse events (SAEs)
- Clinical laboratory test results including coagulation
- Vital signs (heart rate, blood pressure, respiration rate, temperature)
- Abnormal physical examination findings
- Abnormal 12-lead ECG parameters (HR, RR, PR, QRS, QT, QTcB, QTcF)
- Ratings from Investigator visual skin assessments

## 7.3.1 Adverse Event and Prior/Concomitant Medication handling conventions

To handle missing or partial AE and prior/concomitant medication dates, the following rules will be applied.

For partial start dates:

- 1. If the year is unknown, then do not impute the date but assign a missing value.
- 2. If the month is unknown, then:
  - a. If the year matches the year of the first dose date, then impute the month and day of the first dose date.
  - b. Otherwise, assign "January."
- 3. If the day is unknown, then:
  - a. If the month and year match the month and year of the first dose date, then impute the day of the first dose date.
  - b. Otherwise, assign "01."

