- Record concomitant medications taken within 60 days prior to Screening
- Register in IWRS all subjects who become screen failures

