6.1.4 Pregnancy Tests (every 4 weeks \pm 7 days)

- A urine pregnancy test will be collected on WOCBP every month from the day of randomization during the double-blind period to ensure the subject is not pregnant prior to administration of study medication.
 - Due to the COVID-19 pandemic, a urine pregnancy test kit will be sent to WOCBP for in-home testing on a monthly basis. The Investigator (or designee) will contact the subject to review and document the result.

6.1.5 Investigator (or designee) Phone Contact to Subjects (every 4 weeks \pm 3 days)

Following randomization, the investigator (or designee) will contact the subject monthly to assess for:

• Adverse events, concomitant medications and to provide study related reminders regarding eDiary use and/or C213 application instructions in advance of administering study medication for the qualifying cluster attack.

6.1.6 Investigator (or designee) Phone Contact to Subject– Following application of C213 (+ 2 days)

The investigator (or designee) will contact the subject within 2 days after C213 application to assess for:

• Adverse events and to schedule the subject for a final visit 1-8 days after C213 application.

6.1.7 Visit 3 - Day 1-8 Following Treatment of Cluster Headache / End of Study (or Early Discontinuation) Visit (+3 days)

The following procedures will be performed at the Day 1-8 / end of study (or early discontinuation):

- Collect the applicator and any unused patches and perform drug accountability
- Perform physical exam, including weight
- Record vital signs: temperature, respiratory rate (RR), blood pressure (BP), and heart rate (HR)
- Collect blood (4-hr fasting) for clinical laboratory measurements including clinical chemistries, coagulation, hematology, and serum pregnancy for WOCBP
- Collect serum pregnancy for all WOCBP
- Perform 12-lead electrocardiogram (ECG)
- Collect and review subject's eDiary data with the subject for the following:

 Subject compliance with study drug treatment and/or rescue therapy use
- Investigator Skin Assessment
- Record concomitant medications
- Review of adverse events

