6.2.10 Previous, Concomitant and Prohibited Medications

Concomitant medications will be recorded on the appropriate source document and on the appropriate eCRF at all visits including screening, randomization day, and end of study (or early discontinuation). All previous and concomitant medications taken within 90 days prior to the screening visit must be recorded in the source document and eCRF. When new medications are started and come to the attention of the investigator between scheduled visits, they will be recorded that day on the appropriate source document and on the appropriate eCRF.

No triptans or ergots are allowed within 24 hours prior to onset of current cluster headache symptoms. If rescue therapy is required by the subject, rescue therapy other than a triptan or ergot is permitted at or after 20 minutes post study drug administration. Ergots and triptans may be resumed 24 hours after dosing with study medication.

No lotions, ointments or powders applied to the skin immediately before (within an hour) or for 24 hours after applying the patches are allowed.

Table 6 lists all prohibited medications. Medications listed in Table 6 are prohibited from 7 days prior to screening through the final visit.

Table 6: Prohibited Concomitant Medications

Drug Type	Medication
Prescription anticoagulants	Entire class
Monoamine oxidase inhibitors	Entire class
Potent CYP450 3A4 Inhibitors	Ketoconazole
	Erythromycin
	Clarithromycin
	Cimetidine
	Grapefruit
CYP450 1A2 Inhibitors/Inducers	Ciprofloxacin

Drug Type	Medication
	Enoxacin
	Fluvoxamine
	Alpha-Naphthoflavone
	Furafylline
	Omeprazole (OTC)
	Lansoprazole (OTC)
	Fluvoxamine
	Enoxacin
	Phenytoin
	Rifampin
	Ritonavir
	teriflunomide
	Methoxsalen
	Mexiletine
	Tobacco Cigarettes

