#### 11. MEDICATIONS

#### 11.1 Concomitant Medications

All medications will be coded using WHODrug-Global-B3 version March 2019. Prior and concomitant medications will be summarized by treatment group and by the number and percentage of subjects taking each medication, classified by using WHO-DD Anatomical Therapeutic Chemical Level 3 and preferred term.

Prior medications are defined as medications or therapies initiated prior to the start of patch administration. Concomitant medications are defined as any medications other than the study drug that a subject receives concurrently with the study drug. These medications will have start dates on, prior to, or within 5 days after the date of patch administration and end dates on or after the date of patch administration. Any medication that was stopped more than 90 days prior to informed consent will not be considered prior or concomitant.

Prior and Concomitant medications will be summarized. All medications will be presented in a listing.

Please refer to Section 7.3 for the conventions used to impute partial start dates and end dates of concomitant medications.

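### SAP 7.3.1 can impute a medication start date later than its known stop date, so a medicine that ended before dosing appears in neither the prior nor the concomitant table; the prior-medication look-back (60 versus 90 days) also needs reconciling

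*SAP*

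**What the plan says.** **Start-date imputation (SAP 7.3.1).** If the month is unknown: "If the year matches the year of the first dose date, then impute the month and day of the first dose date"; otherwise January is assigned. If only the day is unknown: "If the month and year match the month and year of the first dose date, then impute the day of the first dose date"; otherwise day 01 is used. If the year is unknown, the date stays missing. The same section imputes partial stop dates to December or to the last day of the month.

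**Classification (SAP 11.1).** "Prior medications are defined as medications or therapies initiated prior to the start of patch administration". For concomitant medications: "These medications will have start dates on, prior to, or within 5 days after the date of patch administration and end dates on or after" that same date. A medicine stopped more than 90 days before informed consent is neither. Both classes are summarised by treatment group, and all medications are listed.

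**Fallback rules (SAP 7.3.1).** Four further rules classify medications whose start or stop is missing. They apply after the imputation. The second makes a medicine with a missing start and a stop before the patch day a prior medication.

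**Look-back.** Protocol 6.1.1: "Record concomitant medications taken within 60 days prior to Screening". Protocol 6.2.10: "All previous and concomitant medications taken within 90 days prior to the screening visit must be recorded". SAP 11.1 also works with 90 days, counted from consent.

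**The concern.** Moving an incomplete start date to the dosing date is a familiar way of leaning towards the concomitant class when nothing contradicts it. Here a known stop date can contradict it, and the SAP does not say what happens then. The derived record shows a medicine beginning after it ended, and neither table has a place for it. The result also runs against the information available: a subject who remembers the year is worse recorded than one who remembers nothing about the start.

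Assessment of concomitant medications is a listed safety endpoint (SAP 2.2.2), and the prior and concomitant tables are the only planned by-arm summaries of these data. SAP section 12 says that far fewer subjects were randomised than planned, so one misplaced record moves a percentage further than it would have with about 40 per arm.

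**Working it through.** The plan gives no figure to reproduce; the check is of date logic.

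**Notation.** D = date of patch administration, S = start after imputation, E = stop (known or imputed), C = consent date. From SAP 11.1:

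- prior: S < D
- concomitant: S ≤ D + 5 and E ≥ D
- neither, by design: E < C − 90

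**General result.** Take a medicine with C − 90 ≤ E < D, whose start is partial and falls in the dosing year (month unknown) or the dosing month (day unknown). SAP 7.3.1 sets S = D.

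- Prior needs D < D: false.
- Concomitant needs E ≥ D: false.
- The fallback rules need a date that is still missing. S is not missing, so they do not apply.

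The record is in neither table, for every such choice of D, E and C.

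**Worked records.** The dates are assumed for illustration: C = 1 Jun 2020 and D = 15 Sep 2020, 106 days later and so inside the 48-week treatment period. C − 90 is 3 Mar 2020.

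| Start as recorded | Stop as recorded | Imputed start | Stop used | Class |
|---|---|---|---|---|
| 2020, month unknown | 10 Jul 2020 | 15 Sep 2020 | 10 Jul 2020 | neither (start 67 days after stop) |
| Sep 2020, day unknown | 10 Sep 2020 | 15 Sep 2020 | 10 Sep 2020 | neither |
| 2020, month unknown | Jul 2020, day unknown | 15 Sep 2020 | 31 Jul 2020 | neither |
| year unknown | 10 Jul 2020 | missing | 10 Jul 2020 | prior |
| 1 Jul 2020 | 10 Jul 2020 | 1 Jul 2020 | 10 Jul 2020 | prior |
| 2019, month unknown | 10 Jul 2020 | 1 Jan 2019 | 10 Jul 2020 | prior |
| 2020, month unknown | Sep 2020, day unknown | 15 Sep 2020 | 30 Sep 2020 | concomitant |

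**Enumeration on the same dates.** Stops from 3 Mar (day 63 of the year) to 14 Sep (day 258) are 196 dates. A stop on day b can be paired with b possible starts in the year, so the pairs number 63 + 64 + … + 258 = (63 + 258) × 196 / 2 = 31,458. If the month of the start is unknown, all 31,458 fall in neither table. For an unknown day within September the pairs number 14 × 15 / 2 = 105, and all 105 fall in neither. These counts show that the rule has no exception inside its scope. They are not estimates of affected records.

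**With a cap.** Replace S = D by S = min(D, E). For these records S = E < D, so each is prior and not concomitant, which agrees with the true order of events. Where E ≥ D, or the stop is missing, S stays at D and nothing changes.

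**Look-back.** 90 − 60 = 30 days. A site following Protocol 6.1.1 need not record medicines taken only on days 61 to 90, which is 30/90, one third of the period in Protocol 6.2.10.

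**The case against.** The strongest reply is that nothing leaves the report. SAP 11.1 lists every medication, and with low enrolment a by-subject listing can be read in full. No test uses these tables. Rescue use for efficacy comes from the eDiary (SAP 7.2.4.4), and treatment-emergent status comes from a CRF question, not from dates (SAP 7.3.1 and 10.1). All of this stands and limits the point to table classification.

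It could also be argued that missing, in the fallback rules, includes partial dates, in which case the second rule would return prior. That is the weaker reading: SAP 7.3.1 assigns a missing value only when the year is unknown and applies the fallback rules after imputation.

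A reader might infer more than the documents support:

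- **That every partial start with an early stop is wrongly dropped.** Medicines stopped more than 90 days before consent are left out by design, whatever start is imputed.
- **That the concomitant window is an error because it ends 5 days after dosing**, while Visit 3 may fall up to 8 + 3 = 11 days after. The 5-day limit appears in both SAP 7.3.1 and SAP 11.1 and reads as a deliberate definition. A subject seen by day 5 has no follow-up days outside it. Extending it would be a preference.
- **That ongoing preventives disappear.** An ongoing medicine whose start has an unknown month in the dosing year is classed as concomitant only. It loses its prior flag but stays in a table, and a start in an earlier year keeps both flags.
- **That the comparison of arms at baseline is misstated.** The documents give neither a count nor a direction for this.

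**Conclusion.** The point holds in a narrow form. As written, SAP 7.3.1 can produce a start after a known stop, and such a record meets neither definition in SAP 11.1. This takes three things together: a partial start in the dosing year or month, a stop (known or imputed) before dosing, and a stop not more than 90 days before consent. Within those conditions the misclassification is certain. How often they occur is not in the documents, and the number may be zero.

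The difference between the 60-day and 90-day look-backs is a real inconsistency but a minor one, concerning data collection and not analysis.

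The consequence is confined to the prior-medication summary and to impossible intervals in the derived data. The listing, the efficacy results and the treatment-emergent classification do not change. This is a tidy-up, worth making because it is cheap.

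**What to change.** **SAP 7.3.1.** Add one sentence to the start-date rules: an imputed start date may not be later than the stop date, after any imputation of the stop; if it would be, set the start to the stop date. The affected records then become prior medications. No information is needed on which visit recorded the medicine, and ongoing medicines are handled as now.

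**Look-back.** Reconcile Protocol 6.1.1 with Protocol 6.2.10 and SAP 11.1 so that one period is stated. The SAP (version 1.0, 14 April 2021) already describes enrolment as short of plan, so rewording cannot recover days 61 to 90 for subjects already screened. The study report should say that collection may have differed between sites.

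**Leave alone.** The 5-day concomitant window needs no change. Ending it at Visit 3 would shorten it for subjects seen on days 1 to 4 and leave it undefined for anyone without that visit.

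**Cost.** One SAP sentence, one line of derivation code with a check for starts after stops, and one wording correction. No new assessments.

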## For partial end dates:

- 1. If the year is unknown, then do not impute the date but assign a missing value.
- 2. If the month is unknown, then assign "December."
- 3. If the day is unknown, then assign the last day of the month.

Adverse events are categorized as either pre-treatment adverse events or treatmentemergent adverse events based on the response to the CRF question "Did the AE occur prior to patch administration?"

After implementing the rules above, to determine whether medications with missing start or stop dates are prior or concomitant medications, the following strategy will be used:

Protocol: CP-2019-001 Page 18 of 26

Final Version 1.0

1. If the start date and stop date are both missing, then the medication is considered to be both a prior and a concomitant medication.

- 2. If the start date is missing but the stop date is not missing and is before the day of patch administration, then the medication is considered to be a prior medication, otherwise it is considered to be both prior and concomitant.
- 3. If the stop date is missing but the start date is not missing and is on or within 5 days after the date of patch application, then the medication is considered to be concomitant.
- 4. If the stop date is missing but the start date is not missing and is prior to the date of patch application, then the medication is considered to be both prior and concomitant.

The missing severity of an AE will be imputed to "severe"; the missing relationship to study drug of an AE will be imputed to "related".

#### 8. STUDY SUBJECTS AND DEMOGRAPHICS

#### 8.1 Disposition of Subjects and Withdrawals

The numbers and percentage of subjects randomized, completing the study, and withdrawing from the study, along with reasons for withdrawal, will be tabulated overall and by treatment group. The number and percentage of subjects in each analysis population will be reported.

#### **8.2 Protocol Deviations**

Protocol deviations will be checked on complete data for all subjects, determined during a (blinded) data review meeting before database lock, unblinding, and the final analysis. Protocol deviations are collected on the CRF.

Protocol deviations will be summarized by treatment group for the Safety population. Protocol "violations" are not differentiated from deviations; instead, each deviation is identified either as "major" or "minor" depending upon its potential impact upon the integrity of the study data or the subject's well-being. Any deviation related to the COVID-19 pandemic is required to be entered in the EDC by the investigational site with the word *COVID* entered as prefix to the deviation texts.

Individual subjects with protocol deviations will be listed.

## 8.3 Demographics and Other Baseline Characteristics

Descriptive summaries of the demographic and other baseline characteristics will be completed for all subjects in the safety population by treatment groups.

Descriptive summaries of demographic and other baseline conditions will include:

• Demographics (age, gender, race/ethnicity, height, weight, body mass index (BMI), alcohol use, smoking history, and illicit drug use). In addition to the safety population, these will also be repeated for all randomized subjects and the mITT population.

Protocol: CP-2019-001 Page 19 of 26

Final Version 1.0

• Cluster headache history characteristics such as type (chronic or episodic) and each subject's usual signs and symptoms. The number of years since first cluster headache will be calculated using the following formula: ([year of informed consent]-[year of first cluster attack]).

Medical History will be coded using Medical Dictionary for Regulatory Activities (MedDRA) version 22.0 and summarized by System Organ Class (SOC) and Preferred Term using frequency counts by treatment group.

#### 9. EFFICACY ANALYSES

## 9.1 Primary Efficacy Analysis

The proportion of subjects who achieve pain relief at 15 minutes and the proportion who achieve sustained pain relief from 15 minutes to 60 minutes post patch administration will be analyzed separately using Fisher's Exact test, with missing data imputed using LOCF (see section 7.1.3). The analyses will include all subjects in the mITT population. A significance test of the treatment difference comparing each C213 dose (1.9 mg and 2.8 mg) to placebo will be tested at the two-sided 0.05 level.

## 9.1.1 Sensitivity and Supporting Analyses

The primary analysis may be followed by a sensitivity analysis to investigate the impact of missing data on the treatment estimates.

#### 9.1.1.1 C213 patients as failure and placebo as responder

If performed, this sensitivity analysis will be a repeat of the primary efficacy analysis where C213 patients with missing data will be imputed as non-responders/failures, and placebo patients with missing data as responders. Thus, for the co-primary outcome measure of pain relief at 15 minutes, C213 patients with a missing pain score at 15 minutes will be considered a treatment failure, and placebo patients with missing data at 15 minutes will be considered a responder. For the co-primary outcome measure of sustained pain relief, C213 patients with a missing pain score at any time from 15-60 minutes will be considered a treatment failure, and placebo patients with a missing pain score will be considered a responder only if all other pain scores within 15-60 minutes are not severe or are missing.

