## 7.1.3 Methods for Handling Missing Data

Missing pain and daily activities data for participants in the mITT population will be imputed via last observation carried forward (LOCF). Prior to imputing missing endpoint data for the endpoint sustained pain relief 15-60 minutes, pain relief will be assessed at each of the 15, 20, 30, and 60-minute timepoints that have data available. If any of these

Protocol: CP-2019-001 Page 15 of 26

Final Version 1.0

timepoints has a pain severity rating of moderate or severe, or if the subject has used a rescue medication/therapy, then the subject will be considered to have not achieved sustained pain relief and this endpoint will not be imputed. Otherwise, missing pain data will be imputed using LOCF. Missing data for all sustained pain relief and sustained pain freedom endpoints will be handled this way.

Missing safety data will not be imputed. Due to COVID-19, it is unavoidable that some subjects will be missing certain safety assessments, such as (but not limited to) Visit 3 clinical labs, vital signs, and ECG. This is because the Visit 3 occurred during the pandemic and telemedicine visit was necessary. Safety summaries will be generated using observed data, and missing safety assessments will be captured as protocol deviations.

Missing rescue medication data will be handled as described in section 7.2.4.4.

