#### 7.2.3 Sustained Pain Relief

The other co-primary efficacy endpoint is the proportion of subjects who achieve sustained pain relief from 15 minutes to 60 minutes post patch administration. Sustained pain relief requires a pain rating of mild or none at each timepoint from 15 minutes to 60 minutes without the use of acute rescue medication at any time during the 60 minutes post patch administration.

Protocol: CP-2019-001 Page 16 of 26

Final Version 1.0

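### The only missing-data sensitivity analysis is one optional extreme allocation: it is conclusive if it passes, but a failure does not show where the conclusion tips

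*SAP*

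**What the plan says.** Protocol 7.4.1 leaves missing data and sensitivity analyses to the SAP. SAP 7.1.3 sets the main rule: "Missing pain and daily activities data for participants in the mITT population will be imputed via last observation carried forward (LOCF"). In SAP 9.1 the co-primary endpoints "will be analyzed separately using Fisher's Exact test, with missing data imputed using LOCF", and each dose comparison "will be tested at the two-sided 0.05 level".

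The check on that rule is in SAP 9.1.1: "The primary analysis may be followed by a sensitivity analysis to investigate the impact of missing data on the treatment estimates". SAP 9.1.1.1 gives its content, again on condition that it is performed: "C213 patients with missing data will be imputed as non-responders/failures, and placebo patients with missing data as responders". For sustained relief, a C213 subject with any missing score from 15 to 60 minutes is a failure. A placebo subject with a missing score is a "responder only if all other pain scores within 15-60 minutes are not severe or are missing".

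No intermediate allocation, opposite extreme or tipping-point analysis is specified. The subgroup analysis in SAP 9.3 concerns the change of time zero, not missing data.

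**The concern.** The stated purpose is "to investigate the impact of missing data on the treatment estimates". One allocation at the far end of the possible outcomes serves that purpose only in part. Because it is the least favourable case, passing it settles the matter. Failing it settles little: a result that holds under nearly every allocation and one that holds under fewer than half can both come back as not significant.

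This is the only planned check on LOCF, and it may be skipped. The risk is that a largely robust co-primary result is discounted because of one implausible corner, or that a fragile one is excused on the ground that the worst case is always harsh. The single p-value does not let the reader decide between these.

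A second problem lies in the sustained-relief rule. SAP 7.2.3 says "Sustained pain relief requires a pain rating of mild or none at each timepoint from 15 minutes to 60 minutes", and SAP 7.1.3 makes any observed moderate or severe score, or rescue use, a failure before imputation. SAP 9.1.1.1 bars a placebo subject only for a severe score. A placebo subject with an observed moderate score and another score missing would therefore count as a responder, although the outcome is already known to be failure. For this endpoint the scenario is harsher than a true worst case.

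**Working it through.** **Design figure first.** Inputs from SAP 5: 20% vs 55%, two-sided 0.05, continuity-corrected chi-square, 40 per arm, 15% dropout. Evaluable n = 40 × 0.85 = 34 per arm. Mean proportion = 0.375.

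Power = Φ{[0.35 − 1/34 − 1.96·√(2 × 0.375 × 0.625/34)] / √[(0.20 × 0.80 + 0.55 × 0.45)/34]} = Φ{(0.3206 − 0.2301)/0.1095} = Φ(0.826) = 79.6%.

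The stated figure of about 80% is reproduced.

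**Assumptions.** SAP 12 says that enrolment fell well short but gives no number, and neither document gives the number missing. The 15% dropout is not a guide to missingness within mITT, because SAP 6 already excludes subjects with no score in the first 15 minutes. Arms of 10 to 40 and 1 to 6 missing per arm are therefore assumed.

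**Method.** Take a observed C213 responders, b observed placebo responders, m undetermined subjects per arm and n subjects per arm in total. For i and j each from 0 to m, compute the two-sided Fisher p for (a+i)/n vs (b+j)/n. The worst case is i=0, j=m. There are (m+1)² cells. When known failures are classified first, the LOCF result is itself one of the cells.

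**20 per arm, 2 missing each.** Rows are C213 responders added (0, 1, 2); columns are placebo responders added (0, 1, 2).

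11/18 vs 4/18:

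| | 0 | 1 | 2 |
|---|---|---|---|
| 0 | 0.048 | 0.105 | 0.200 |
| 1 | 0.022 | 0.054 | 0.111 |
| 2 | 0.010 | 0.025 | 0.056 |

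Four of 9 are below 0.05. The result is lost even when one missing subject responds in each arm.

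12/18 vs 3/18:

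| | 0 | 1 | 2 |
|---|---|---|---|
| 0 | 0.008 | 0.023 | 0.054 |
| 1 | 0.003 | 0.010 | 0.025 |
| 2 | 0.001 | 0.004 | 0.010 |

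Eight of 9 are below 0.05. Only the extreme corner fails.

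13/18 vs 3/18: the worst case is 13/20 vs 5/20, p=0.025, and all 9 are below 0.05.

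**Planned sizes.**

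| n per arm | missing per arm | observed | cells below 0.05 | worst p |
|---|---|---|---|---|
| 34 | 3 | 17/31 vs 6/31 | 15 of 16 | 0.080 |
| 34 | 3 | 19/31 vs 6/31 | 16 of 16 | 0.026 |
| 40 | 6 | 17/34 vs 7/34 | 28 of 49 | 0.49 |
| 40 | 6 | 19/34 vs 7/34 | 39 of 49 | 0.25 |
| 40 | 6 | 24/34 vs 7/34 | 49 of 49 | 0.024 |

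The first row is the design effect: 0.55 × 31 ≈ 17 and 0.20 × 31 ≈ 6.

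**How often the check passes.** This is the chance that a result significant among subjects with observed outcomes stays significant in the worst case, by exact binomial enumeration. Significance among observed outcomes stands in for the LOCF result, which cannot be simulated from the documents.

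| true rates | n per arm | 1 missing | 2 missing | 3 missing | 6 missing |
|---|---|---|---|---|---|
| 55% vs 20% | 40 | 92% | 80% | 66% | 21% |
| 55% vs 20% | 20 | 64% | 34% | 13% | – |
| 55% vs 20% | 10 | 16% | 1% | – | – |
| 75% vs 20% | 20 | 87% | 66% | 39% | – |

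**The case against.** A worst-case allocation is a transparent, conservative bound, and passing it is stronger evidence than most alternatives. It would not stand alone either: the LOCF result sits beside it, and the p-values differ (0.200 for the fragile example, 0.054 for the robust one). SAP 7.1 promises frequencies and percentages for the primary variables, so proportions by arm would probably be shown. SAP 1 and 4.2 also allow further analyses labelled as post hoc.

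Most of this stands. It would be wrong to say that the check yields no estimate at all; what SAP 9.1 lacks is an odds ratio or confidence interval. Two points, LOCF and the extreme, still do not show where between them the conclusion changes, and the size of the worst-case p does not reveal it: 0.080 goes with 15 of 16 cells significant at 34 per arm, and 0.25 with 39 of 49 at 40 per arm. A grid chosen after unblinding would carry less weight than one fixed in the plan.

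A reader might go further and infer that, at this trial's size, the check must return a non-significant result whatever the data. The documents do not support that. They give neither the size nor the number missing, and 13/18 vs 3/18 passes at the assumed 20 per arm. A reader might also infer that low enrolment causes the problem. It makes an uninformative failure more likely, but 17/31 vs 6/31 shows the same pattern at planned evaluable size. In very small arms the larger difficulty is power: at the design rates 10 per arm gives 6/10 vs 2/10, p=0.17, with nothing missing.

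**Conclusion.** The point holds in limited form. The plan's single, optional extreme allocation is informative only when it passes; a failure does not separate a result that tips under a mild departure from LOCF from one that tips only at the corner. The illustrations rest on assumed sizes and missing counts, equal across arms. How often the check would fail depends strongly on both: from 8% of significant results (40 per arm, 1 missing each, design rates) to 99% (10 per arm, 2 missing each).

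Separately, and with no assumption about size, the placebo rule for sustained relief conflicts with SAP 7.1.3 and 7.2.3 on observed moderate scores.

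Neither point undermines the primary analysis. This is a cheap improvement to its one planned robustness check.

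**What to change.** In SAP 9.1.1, make the analysis mandatory. In 9.1.1.1, replace the single allocation with a tipping-point grid for each dose against placebo and each co-primary endpoint:

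- Classify known outcomes first. For sustained relief, any subject in either arm with an observed moderate or severe score from 15 to 60 minutes, or with rescue use, is a failure, as SAP 7.1.3 and 7.2.3 already require. This replaces the rule that bars only severe scores in placebo subjects.
- Let responders among the m1 undetermined C213 subjects run over 0 to m1, and among the m0 undetermined placebo subjects over 0 to m0.
- Report the difference in proportions and the Fisher p-value in each of the (m1+1)(m0+1) cells, mark where the conclusion changes, and mark the LOCF cell.

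With known failures removed first, the worst case becomes a true corner of the grid, so the bound the SAP wanted is kept. The cost is SAP wording, a short loop around the existing Fisher program, and one small table per comparison with a sentence of interpretation. No new data are needed and trial conduct is unaffected.
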